The purpose of this 8-week double-blind randomized placebo-controlled study is to assess the tolerability, safety, and efficacy of tPBM in adult patients with ASD. Based on our central hypothesis that tPBM will be safe, tolerable, and effective in improving ASD symptoms in adults, we propose to enroll up to 27 participants of both genders ages 18-50 years with intact intellectual functions satisfying DSM-5 criteria for ASD.

Primary Aims:

Aim 1. To examine the clinical efficacy and safety of tPBM in patients with ASD. We will study the short- and long-term clinical effects of tPBM in 27 adults with ASD by conducting an 8-week randomized clinical trial (RCT).

Secondary Aim:

Aim 1. Explore anti-inflammatory biomarker response to tPBM treatment. We will examine any relationship to ASD symptom severity before and after the 8-week treatment course.

Aim 2. To study the treatment effect of tPBM on mood, social cognition, executive function, ADHD, depression and anxiety symptoms in adults with ASD.

3. General Description of Study Design

This study is a double-blind, placebo-controlled, sequenced parallel study on the use of tPBM as treatment for ASD symptoms in adult patients. This study will last up to 12 weeks from enrollment (allowing up to four weeks from the date of consent to schedule and complete the initial screening process).

4. Subject Selection

Subjects diagnosed with ASD who meet all inclusion criteria, have none of the exclusion criteria, and are willing to undergo the Informed Consent process will be eligible to participate in this clinical study.

Inclusion Criteria

Subjects may be included in the study only if they meet all of the following criteria:

- Male or female participants between 18 and 50 years of age (inclusive)
- Fulfills DSM-5 diagnostic criteria for autism spectrum disorder as established by the clinical diagnostic interview.
- Participants with at least moderately severity of ASD symptoms as demonstrated by SRS raw score ≥ 85 and CGI-ASD severity score ≥ 4

- Participants must understand the nature of the study. Participants must be deemed not to have impaired decision-making capacity and must have the capacity to provide direct informed consent. Participants must sign an IRB-approved informed consent form before initiation of any study procedures.

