- Investigator and his/her immediate family, defined as the investigator's spouse, parent, child, grandparent, or grandchild.

Source of Subjects

We plan to enroll up to 54 adults in order to achieve the goal of exposing up to 27 subjects. We plan to recruit participants from the referral pool of existing and new patients attending a specialty clinic for ASD at the Massachusetts General Hospital.

The Alan and Lorraine Bressler Clinical and Research Program for Autism Spectrum Disorder is a specialized ambulatory care program devoted to the assessment and treatment of individuals of all ages with ASD. It is one of only a few programs in the New England area to offer comprehensive assessment for individuals with ASD, including a complete psychiatric evaluation, psychopharmacological, neuropsychological, behavioral, and social services consultation, psycho-educational support and cognitive/behavioral therapies. The ambulatory care team consists of board-certified psychiatrists specialized in the assessment and management of ASD. Adults with ASD, the majority of whom are individuals with intact intellectual capacity and language skills, make up approximately one-third of the ASD population attending the clinic.

If a potential subject's clinician ascertains that the patient has an interest in study participation, the clinician will offer contact information for the study coordinator to the patient. The patient can then contact the study coordinator for more information on the trial. All subjects that enter the study will undergo standard screening and diagnostic procedures. Clinical records are not scanned in order to recruit subjects. Patients who potentially meet criteria for the study will only be contacted by their treating clinician and referred should the patient decide they wish to participate. If a patient of an investigator decides to enroll in the trial, the process of informed consent will be conducted with a co-investigator who does not treat the patient in a clinical setting. Under no circumstances will a physician investigator obtain informed consent from his or her own patient.

Subjects who have completed a previous clinical trial in our program may be eligible to participate in this study, as described in the Subject Enrollment section. Other medical records on a subject will not be used at any point during this study.

5. Subject Enrollment

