why they are receiving this form and further instructions. Study staff will schedule a time for the subject to meet with a study clinician via phone to complete the consent. The study clinician will have a conversation by phone with the subject to obtain consent in the usual fashion: review the consent form, review the inclusion and exclusion criteria, review risks and benefits of the study, review alternatives to participation, and answer any questions subjects may have. The informed consent documents will be used to explain, in simple terms, the risks and benefits of study participation to the subject. Only subjects who can consent for themselves will be included in this study. The nature of the study will be fully explained to the subject by a board-certified physician who is either the principal investigator or a co-investigator. The subject will be encouraged to ask questions pertaining to their participation in the study and the subject may take as much time as they feel necessary to consider their participation in the study and to consult with family members or their physician. If the subject decides to participate, they will sign the consent form using Adobe eSignature. The study clinician will also sign the consent form using Adobe eSignature prior to beginning any study procedures. Subjects will be sent a copy of the signed form by email for their records. Any subject that signs Informed Consent will be considered enrolled into the study, although they may not participate if they do not qualify for the study. Participation in this study is voluntary and subjects may withdraw from the study at any time. If a subject's ability to comprehend and communicate is compromised (per assessment of the Investigator), local regulations pertaining to Informed Consent signatures should be followed.

If a potential subject's clinician ascertains that the patient has an interest in study participation, the clinician will offer contact information for the study to the patient and/or their parent/guardian. The patient and/or their parent/guardian can then contact the study coordinator for more information on the study. If the patient's physician is a member of study staff, the patient and his/her family will also be offered the opportunity to speak with another study physician who is not their treating clinician to review study details and consider participation. Clinical records are not scanned in order to recruit subjects.

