6. STUDY PROCEDURES

After providing written informed consent, all subjects will complete a clinical diagnostic interview via a virtual visit with a board-certified study clinician to assess eligibility. A study clinician will complete the Reproductive Potential Form. All subjects will be administered an assessment battery including a brief demographic interview and the SRS-2 (Pre-Screening). If an additional family member of the subject is available, we will ask that family member to independently complete an SRS-2 form. Both forms will be scored and the form with the higher score will be used to determine subject eligibility in order to reduce the possibility of under-recognition of social impairment.

We anticipate that subjects may enter this study following completion of/withdrawal from other ASD protocols in our office, and that there may be procedural overlap. So as to not burden subjects/parents/guardians with redundant time commitments, we will use the following diagnostic data previously collected: If a subject has completed an evaluation with one of the study clinicians and/or the structured diagnostic assessment in the three years prior to entrance into this study, he/she will not be asked to repeat any overlapping diagnostic procedures. We will use the study diagnostic data that had been previously collected so as to not burden the subject with redundant time commitments.

However, the study clinician will review the interval time period to assess for clinically significant medical or psychiatric history, to ensure that the subject meets appropriate study entrance criteria.

All female subjects of childbearing potential will have a urine pregnancy test that will be mailed to their address prior to Screening visit. If a participant has a positive urine pregnancy test, she will not be able to take part in the study. The study doctor will inform the participant of any positive test results.

Upon completion of Informed Consent, subjects will be randomized to receive either tPBM or sham and the respective device will be mailed. This study will include up to 27 subjects randomized at 1:1 ratio into 2 groups: tPBM and Sham.

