54 subjects will be randomized (1:1) into the tPBM or placebo/sham group and be treated for 8 weeks post randomization. This design largely protects against the bias introduced by confounding factors.

We will rely on comparisons of the participants' performances in each study arm (placebo/sham and tPBM) at baseline prior to the initiation of treatment relative to their scores at the last assessment (completion/drop-visit). Since we are following subjects over a short period, missing data are not expected to impact our analyses such that standard statistical analyses will be employed. Specifically, we will employ longitudinal mixed-effects regression models (RM) with random effects for the subjects using Stata 16.0 (StataCorp, 2019). The RMs will use robust standard errors to account for the repeated measures on each subject. We will test binary data using mixed-effects logistic RMs, count data with mixed-effects Poisson RMs, and normally distributed data with mixed-effects linear RMs. Each model will predict outcome scores from treatment group (placebo/sham or tPBM), study visit (continuous predictor), and the treatment group-by-study visit interaction. All analyses will be intent to treat (ITT).

10. Monitoring and Quality Assurance

Consistent with good clinical practice, safety will be monitored at each study visit by a subject's assigned clinician. This clinician will be available 24 hours a day by page. The principal investigator will supervise all study activities including ratings and reported adverse events. All procedures have been designed to minimize subject discomfort, and no subject will be asked to engage in research procedures not outlined in the consent form.

Safety will be monitored through treatment-emergent adverse events. Subjects will be monitored for adverse events at each visit. All adverse events will be recorded. A subject may be dropped from the study or dosage may be decreased at any time due to adverse events. All adverse events will be reported to the PHRC according to PHRC guidelines. All concomitant medications will be assessed at every study visit.

All adverse events will be recorded from the time of Informed Consent through study completion, or termination. The Adverse Event CRF must be completed and submitted to the IRB and Niraxx, as required. Regulations for adverse event handling and reporting contained in the FDA and ICH Guidelines will be adhered to.

Overview and Definitions

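### Section 9 randomises 54 subjects, but Section 6 caps randomisation at 27 and Primary Aim 1 places the trial in 27 adults

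*Combined protocol and SAP*

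**What the plan says.** Five statements bear on the size of the trial.

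- Section 9, Statistical Analysis: "54 subjects will be randomized (1:1) into the tPBM or placebo/sham group and be treated for 8 weeks post randomization".
- Section 6, Study Procedures: "This study will include up to 27 subjects randomized at 1:1 ratio into 2 groups: tPBM and Sham".
- Section 2, Specific Aims and Objectives, has two. The statement of purpose says "we propose to enroll up to 27 participants of both genders ages 18-50 years", and Primary Aim 1 places the 8-week randomised trial in 27 adults with ASD.
- Section 4, Source of Subjects: "We plan to enroll up to 54 adults in order to achieve the goal of exposing up to 27 subjects".

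Section 5, Subject Enrollment, gives the word enrolled a specific meaning: "Any subject that signs Informed Consent will be considered enrolled into the study". This applies even to people who then turn out not to qualify. Section 6 places randomisation after consent. Section 9 makes every analysis intent to treat.

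The protocol states no significance level, power, target effect, standard deviation or expected dropout rate.

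**The concern.** Sections 6 and 9 count the same event, 1:1 allocation to tPBM or sham, and arrive at different totals. Section 6 gives a ceiling, so 54 cannot be a permissible value within it.

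Section 9 is the only statistical plan in the document. With intent-to-treat analysis, the number randomised fixes the planned size of the analysis set, and that section gives twice the figure in the randomisation text. Two practical consequences follow. If recruitment stops at 27, one section says the target was met and another says it was half met. If a 28th subject is randomised, Section 9 permits it and the Section 6 ceiling is breached. Neither completion nor adherence to the planned size can be judged against the protocol as it stands.

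**Working it through.** **1. Can either figure be reproduced?** No. The inputs to a sample size calculation are not given, so neither 27 nor 54 can be derived, and the check is a comparison of stated counts: 54/27 = 2.

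**2. Does any single reading fit every statement?**

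| Statement | Reading A: 54 consented, 27 randomised | Reading B: 54 randomised, 27 of them on active tPBM |
|---|---|---|
| Section 2, purpose: enrol up to 27 | Conflicts, given the Section 5 definition | Conflicts |
| Section 2, Primary Aim 1: trial in 27 adults | Fits | Conflicts |
| Section 4: enrol 54 to expose 27 | Fits, if exposure includes sham | Fits, if exposure means active light |
| Section 5: enrolled means consented | Fits | Leaves no room for screen failures within 54 |
| Section 6: up to 27 randomised into two groups | Fits | Conflicts |
| Section 9: 54 randomised and treated | Conflicts | Fits |

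Reading A fits better, but neither fits everything. Reading B cannot be dismissed outright: 54 at 1:1 gives exactly 27 on active treatment, whereas 27 is odd and can only be split 14 and 13.

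**3. What the factor of two means for precision (illustration only).** The assumptions are mine: two-sided alpha 0.05, a two-sample t-test with equal SDs, and effects in SD units. This is not the mixed model that Section 9 plans.

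- 95% CI half-width = t(0.975; n1+n2−2) × √(1/n1 + 1/n2). For 14 and 13: 2.060 × 0.385 = 0.793 SD. For 27 and 27: 2.007 × 0.272 = 0.546 SD.
- The detectable effect d is the value at which a noncentral t variable with n1+n2−2 degrees of freedom and noncentrality d × √(n1·n2/(n1+n2)) exceeds the critical value with probability 0.80.
- Assumed 20% dropout: 27 × 0.8 = 21.6, taken as 22 (11 and 11); 54 × 0.8 = 43.2, taken as 43 (22 and 21).

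| Scenario | Per arm | Detectable effect, 80% power (SD) | 95% CI half-width (SD) |
|---|---|---|---|
| 27, no dropout | 14/13 | 1.123 | 0.793 |
| 54, no dropout | 27/27 | 0.777 | 0.546 |
| 27, 20% dropout | 11/11 | 1.256 | 0.889 |
| 54, 20% dropout | 22/21 | 0.875 | 0.616 |

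Without dropout the ratios are 1.123/0.777 = 1.445 and 0.793/0.546 = 1.452. With 20% dropout they are about 1.44 for both measures. At a true effect of 0.8 SD with no dropout, power is about 52% with 27 subjects and 82% with 54.

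**The case against.** The strongest reply is that only one sentence is out of line. Sections 4, 5 and 6 and Primary Aim 1 together describe up to 54 consented and up to 27 randomised, and Section 9 alone puts 54 in the randomised set, perhaps because the enrolment ceiling was carried over. That is plausible and is the reading I favour. The protocol does not say so, however, and the sentence sits in the section that governs the analysis.

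A second point is that an intent-to-treat denominator is whoever is actually randomised. The models, the visit term and the robust standard errors in Section 9 read the same at 27 or 54, and the one numeric stopping rule is a proportion of the active arm. This is correct. What the contradiction affects is the planned size and the recruitment target, not the form of the analysis.

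Third, the precision figures rest on assumptions that the protocol does not make, so they contradict nothing in it. This also stands. They show scale only, and the finding does not depend on them.

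Finally, the statement in Section 2 about enrolling 27 conflicts with Section 4 only through the Section 5 definition and may be loose wording. It is secondary, but it should be corrected in the same pass.

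**Conclusion.** The protocol is wrong as written on the number randomised. Sections 6 and 9 cannot both hold, and they differ twofold. This follows from the text alone, without any statistical assumption. The documents favour 27 randomised out of up to 54 consented but do not establish it, and the absence of a sample size rationale means nothing else can decide. Under the assumptions given above, the choice changes the detectable effect and the confidence interval width by a factor of about 1.4 to 1.5. The number randomised is a basic trial parameter, so this must be corrected.

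**What to change.** State two separately defined numbers, the maximum consented and the maximum randomised, and give the second in total and approximately per arm. Then use them consistently.

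- **If 27 randomised is intended:** change Section 9 to say that up to 27 subjects will be randomised 1:1 (about 14 and 13), describe the 54 in Section 4 as the consent ceiling including screen failures, and replace enrol with randomise in the Section 2 statement of purpose. Section 6 stays as it is. This is a wording amendment with no effect on design or procedures.
- **If 54 randomised is intended:** correct Sections 2, 4 and 6 instead. This costs more, because it doubles the ceiling in Section 6. Since screen failures count as enrolled under Section 5, the ceiling of 54 in Section 4 would probably have to rise too.

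The point asks for no additional patients. It asks the investigators to say which of their existing figures holds.

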Primary outcome measure of efficacy will be reduction in ASD symptoms as measured by change from baseline on the clinician-rated SRS-2. Responders will be defined as those who demonstrate a $\geq 25\%$ reduction in SRS-2 total score *and* a score of 2 or 1 on the CGI-ASD-Improvement subscale ("much" or "very much improved").

Secondary outcome measure:

1. Treatment-related changes in associated psychopathology, social cognition, executive functions will be assessed by:
 - MGH Social-Emotional Competence Scale (MGH-SEC Scale; clinician- & observer-rated)

- Social Responsiveness Scale-Second Edition (SRS-2; self- & observer-rated)
- Adult Behavior Checklist (ABCL; self- & observer-rated)
- Behavior Rating Inventory of Executive Function-Adult Self Report Version (BRIEF-A) or parent version (BRIEF-P) for youth
- Adult ADHD Self-Report Scale (ASRS) & clinician-rated Adult ADHD Investigator Symptom Report Scale (AISRS) and CGI-ADHD scale
- Quality of Life Enjoyment and Satisfaction Questionnaire (Q-LES-Q)
- Hamilton Anxiety scale (HAM-A) & clinician-rated CGI-Anxiety scale
- Hamilton Depression scale (HAM-D) & clinician-rated CGI-Depression scale

2. Safety and tolerability will be assessed by:

- The monitoring of spontaneous treatment-emergent adverse events with the Clinician-rated Treatment-emergent Adverse Events Log (CTAE)
- tPBM Self-Report Questionnaire (TSRQ)

SAFETY

Consistent with good clinical practice, safety will be monitored at each study visit by a subject's assigned clinician. This clinician will be available 24 hours a day by page. The principal investigator will supervise all study activities including ratings and reported adverse events. All procedures have been designed to minimize subject discomfort, and no subject will be asked to engage in research procedures not outlined in the consent form.

If study participation is discontinued due to safety reasons, participants will receive three follow-up visits, giving adequate time for appropriate psychiatric care to be arranged.

Study Treatment

Safety will be monitored through treatment-emergent adverse events and subject rated TSRQ responses. Subjects will be monitored for adverse events at each visit. All adverse events will be recorded. A subject may be dropped from the study or dosage may be decreased at any time due to adverse events. All adverse events will be reported to the PHRC according to PHRC guidelines. All concomitant medications will be assessed at every study visit.

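### Section 9 prescribes robust standard errors without a small-sample correction or degrees of freedom; with about 27 subjects, tests of continuous outcomes are mildly too liberal if read against a normal distribution

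*Combined protocol and SAP*

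**What the plan says.** Section 9 (Statistical Analysis) plans "longitudinal mixed-effects regression models (RM) with random effects for the subjects using Stata 16.0", with "normally distributed data with mixed-effects linear RMs" and logistic or Poisson versions for binary and count data. One sentence covers the variance for all of them: "The RMs will use robust standard errors to account for the repeated measures on each subject". The predictors are treatment group, "study visit (continuous predictor), and the treatment group-by-study visit interaction". The primary outcome, in the Data Analysis part of section 6, is continuous: "Primary outcome measure of efficacy will be reduction in ASD symptoms as measured by change from baseline on the clinician-rated SRS-2".

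The plan is silent on REML or ML, denominator degrees of freedom, z or t reference, any bias correction of the robust variance, alpha and sidedness.

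The number of subjects is given in two ways. Section 6 says "This study will include up to 27 subjects randomized at 1:1 ratio into 2 groups: tPBM and Sham", section 2 also gives up to 27, and section 4 (Source of Subjects) says "We plan to enroll up to 54 adults in order to achieve the goal of exposing up to 27 subjects". Section 9 says "54 subjects will be randomized (1:1) into the tPBM or placebo/sham group and be treated for 8 weeks post randomization".

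**The concern.** The sandwich variance is justified when there are many independent clusters. Here the clusters are subjects, with 13 or 14 per arm if 27 are randomized. At that size it has two weaknesses. Its expectation lies below the true variance, and it is itself estimated with appreciable error, so that a normal reference is too narrow. Both push the same way: p-values too small and intervals too short, which favours declaring an effect. One sentence governs every mixed model, so the weakness reaches the primary SRS-2 analysis and all continuous secondary scales. It is greater for the observer-rated scales, which are optional and will have fewer subjects.

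**Working it through.** The plan gives no power calculation, alpha or interval to reproduce, so the check concerns the operating characteristics of the stated estimator.

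**Inputs from the documents.** Robust errors, subject random effects and a group-by-continuous-visit interaction (section 9); 27 subjects at 1:1, taken as 14 and 13 (section 6), or 54, taken as 27 and 27 (section 9); three scheduled SRS-2 self-reports, two for the observer scales, and CGI and GAF at every visit (Table II).

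**Assumptions.** Two-sided 5% test; 11 against 11 to represent dropout; 7 against 6 for an informant subset. For the mixed-model simulation: between-subject SD 1, residual SD 0.6, slope SD 0 or 0.6 over 8 weeks, dropout 0% or 20%.

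**Step 1, bias.** With complete data on common visits, the interaction estimate is the difference in mean per-subject slopes. Let G be the total number of subjects. With the factor G/(G-1), the expected robust variance divided by the true variance is

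r = [G/(G-1)] × [(n1-1)/n1² + (n2-1)/n2²] / [1/n1 + 1/n2].

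For 14 and 13: (27/26) × (13/196 + 12/169) / (1/14 + 1/13) = 1.0385 × 0.13733 / 0.14835 = 0.961. The variance is about 4% low and the standard error about 2% low (√0.961 = 0.980).

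**Step 2, type I error.** The robust statistic behaves as t(G-2)/√r, exactly for equal arms and very nearly for 14 and 13.
- Against z: P(|t25| > 1.960 × 0.980 = 1.922) = 6.6%, so coverage is 93.4%.
- Against t(25): P(|t25| > 2.060 × 0.980 = 2.019) = 5.4%.
- Critical value needed: 2.060/0.980 = 2.10. A z interval has 1.960/2.10 = 0.93 of the required width.
- A statistic of 2.2 has nominal p = 0.028; its actual p is P(|t25| > 2.2 × 0.980 = 2.157), about 0.041.

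| Subjects per arm | r | Type I error, z | Type I error, t(G-2) | Critical value needed |
|---|---|---|---|---|
| 14 v 13 | 0.961 | 6.6% | 5.4% | 2.10 |
| 11 v 11 | 0.952 | 7.0% | 5.5% | 2.14 |
| 7 v 6 (assumed) | 0.915 | 8.8% | 5.9% | 2.30 |
| 27 v 27 | 0.981 | 5.8% | 5.2% | 2.03 |

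Simulations of the same quantity with 400,000 null draws agree to about 0.1 point. Without the G/(G-1) factor, 14 v 13 gives 7.0% against z.

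**Step 3, the mixed model itself.** Random-intercept ML fits with a subject-level sandwich were run on about 8,000 null trials per scenario (Monte Carlo error about 0.3 points). For 14 v 13 and z, three-visit scales gave 6.7% to 7.3%, two-visit scales 6.5% to 7.6%, and seven-visit CGI/GAF 5.8% to 7.3%. With t(G-2) the range over all of these was 4.8% to 6.2%. For 27 v 27, three visits and z, it was 5.6% to 5.8%.

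**Step 4, is dropping the robust option a repair?** A random-intercept model with model-based errors and z, 14 v 13, complete data, gave 6.1% at three visits with no slope variation and 9.1% with slope SD 0.6. At seven visits the figures were about 5.4% and 11.3%. It can therefore be worse than the robust test, but by an amount that depends on a slope variance the documents do not give.

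**The case against.** A reader might infer that the plan commits to a normal reference. It does not: section 9 names the software and the robust errors, and nothing about z, t or degrees of freedom. This matters, because moving from z to t(25) removes most of the excess (6.6% to 5.4%). The point must therefore stay conditional: the plan leaves the reference open and names no correction. What remains under t is the downward bias of the variance, which is small.

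A reader might also take 27 clusters as settled. Section 9 states that 54 will be randomized. Sections 2, 4 and 6 make 27 the better-supported count, since section 4 treats 54 as the number enrolled so that 27 are exposed, but the documents do conflict. At 54 the excess is under one point.

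The excess is modest even at 27. The 8.8% figure rests on an assumed informant subset, because the documents say only that observer ratings are optional. Nor do the documents support a fixed error rate for a random-intercept z test. With no slope variation, that test was closer to nominal than the robust z test at three visits (6.1% against 6.7%).

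Finally, a single replacement rule written for linear models would leave the logistic and Poisson models without any variance statement. These objections limit the size of the point and shape the remedy. They do not remove the gap.

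**Conclusion.** The point holds in conditional form. Section 9 prescribes a large-sample variance for a small trial and does not say how it will be corrected or what it will be referred to. At about 27 subjects, the group-by-visit test read against z has a type I error of about 6.5% to 7.5% for the primary outcome, an excess of roughly 1.5 to 2.5 points, and 95% intervals cover about 93%.

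The direction was the same in every scenario run with z. The exact sizes rest on a two-sided 5% level, near-equal arms and, for the simulated ranges, assumed variance components and dropout. This should be corrected before analysis, but it does not by itself invalidate the design.

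**What to change.** **Linear outcomes.** Fit by REML with Kenward-Roger or Satterthwaite degrees of freedom, and choose the covariance by the number of visits:
- Two- and three-visit scales, including SRS-2: unstructured within-subject covariance. For the two-visit observer scales, random intercept, random slope and residual variances cannot be separated, so a random-slope model is not an option there.
- CGI and GAF: random intercept and slope. An unstructured matrix would need 8 × 9 / 2 = 36 parameters at eight visits, or 7 × 8 / 2 = 28 at seven, on about 27 subjects.

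An equally acceptable alternative is to keep robust errors with a bias-reduced (CR2) correction and Satterthwaite degrees of freedom. Do not simply remove the robust option and use a random-intercept z test.

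**Logistic and Poisson models.** Leave their variance statement in place, or give them a small-sample correction of their own.

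**Also state** alpha, sidedness and the reference distribution, and reconcile 27 with 54 across sections 2, 4, 6 and 9.

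**Cost.** A short paragraph in section 9 and outcome-specific model options. Intervals become about 5% to 10% wider at 27 subjects; for 14 v 13 and complete data the factor is 2.10/1.96 = 1.07.

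### Section 9 does not adjust the SRS-2 comparison for baseline or define the baseline record; adjusting is cheap, but the gain is small once the SRS entry cut is allowed for

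*Combined protocol and SAP*

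**What the plan says.** Section 9 (Statistical Analysis) specifies mixed-effects models with subject random effects for all outcomes. Its only fixed effects are these: "Each model will predict outcome scores from treatment group (placebo/sham or tPBM), study visit (continuous predictor), and the treatment group-by-study visit interaction". It lists no baseline covariate, numeric visit coding, primary coefficient or time point. On inference it says "The RMs will use robust standard errors to account for the repeated measures on each subject". Its prose describes comparing, by arm, the pre-treatment scores with those at the last assessment, whether that is completion or drop-out.

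The Data Analysis section makes change from baseline in SRS-2 the primary efficacy outcome, without naming a week.

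The documents place the first SRS-2 differently:

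- Section 5 (Subject Enrollment) has it completed online before informed consent.
- The Screening Visit in section 6 lists it at Week 99, labelled as pre-screening.
- Table II marks the self-report form at screening, Week 4 and Week 8, with no mark at Week 0. It marks the observer form at screening and Week 8 only.
- The Subject-Rated Measures list says baseline, midpoint and final visits.

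Entry requires "SRS raw score ≥ 85 and CGI-ASD severity score ≥ 4". On sample size, section 9 says "54 subjects will be randomized (1:1) into the tPBM or placebo/sham group" while section 6 says "This study will include up to 27 subjects randomized at 1:1 ratio into 2 groups: tPBM and Sham".

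**The concern.** In a randomised trial the true baseline means of the two arms are equal, so a chance baseline imbalance is noise. A model that treats baseline only as the first response subtracts that imbalance in full, whatever the correlation between baseline and Week 8. Conditioning on baseline removes only the part that predicts Week 8, and is usually more precise. In a trial of 27 or 54 people, precision that needs no new data is worth having.

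The second issue is clarity. A slope over continuous time needs a number for every visit. The visit that serves as SRS-2 baseline is labelled Week 99, lies an unstated time before treatment, and is described in two ways. Whoever fits the model must choose its time value, and that choice changes the reported effect.

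**Working it through.** **Inputs.** From the documents: the model terms, 1:1 allocation, SRS-2 occasions, the entry cut, and N = 27 or 54. Not in the documents, and therefore assumed: baseline–Week 8 correlation r of 0.5 to 0.8, the SD ratio, and an entry cut at the population median. Self-report is taken as the form analysed, because it is the only one with a Week 4 score.

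**Step 1: what the planned contrast is.** With visits at 0, 4 and 8, complete data and a random intercept, the slope weights are the centred times: -4, 0, 4. Week 4 gets no weight, and 8 × interaction is the between-arm difference in (Week 8 minus baseline). A model fitted to simulated data confirmed this: -0.03783 by both routes.

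**Step 2: variance ratio.** Set the Week 8 SD to 1 and the baseline SD to k.

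- Change score: 1 + k² - 2kr = (1 - r²) + (k - r)².
- Adjusted for baseline: 1 - r², times (N-3)/(N-4) for estimating the coefficient with a normal baseline. This factor is 24/23 = 1.043 at N = 27 and 51/50 = 1.020 at N = 54.
- Ratio, adjusted/change: (1 - r²)/[(1 - r²) + (k - r)²] × (N-3)/(N-4).

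The first factor never exceeds 1, so for a normal baseline the worst-case loss is 4.3% (N = 27) or 2.0% (N = 54), reached when r = k.

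**Step 3: equal SDs, no restriction (k = 1).** The first factor becomes (1 + r)/2. At r = 0.5 and N = 27, 0.75 × 1.043 = 0.783.

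**Step 4: entry cut on self-report.** Let r be the correlation and the SDs be equal before selection. Cutting a normal baseline at its median leaves a variance of v = 1 - 2/π = 0.363. The first factor becomes (1 + r)/[(1 + r) + v(1 - r)]. At r = 0.5 this is 1.5/(1.5 + 0.182) = 0.892, and × 1.043 gives 0.931. The normal-theory factor is approximate here, but simulation (40,000 runs per cell) agreed with every restricted cell to within 0.01.

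| r | N=27, cut | N=54, cut | N=27, no cut | N=54, no cut |
|---|---|---|---|---|
| 0.5 | 0.931 | 0.910 | 0.783 | 0.765 |
| 0.6 | 0.957 | 0.935 | 0.835 | 0.816 |
| 0.7 | 0.981 | 0.959 | 0.887 | 0.867 |
| 0.8 | 1.003 | 0.980 | 0.939 | 0.918 |

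As extra participants (N/ratio - N) at r = 0.5: with the cut, 27/0.931 - 27 = 2.0 or 54/0.910 - 54 = 5.3; without it, 7.5 or 16.6.

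Eligibility uses the higher of two SRS-2 forms where a family member completes one. This loosens the restriction on self-report. Under an assumed self–informant correlation of 0.3 to 0.5, the simulated gain lies between the two cases: 15–18% falling to 3–4% (N = 27), and 17–20% falling to 5–6% (N = 54).

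**Step 5: coding of the first visit.** Suppose that visit is coded -4. The centred times for -4/4/8 are -6.67, 1.33, 5.33, with sum of squares 74.67. Take the Week 8 effect as 1 and the Week 4 effect as w. Then 8 × slope = 8(1.33w + 5.33)/74.67, which is 0.57, 0.64 or 0.71 for w = 0, 0.5 or 1. Signal-to-noise relative to 0/4/8 coding is 87%, 98% or 109%. The size of the estimate moves clearly. The test moves modestly, in either direction.

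**The case against.** The strongest reply is that the planned test is sound and the gain rests on quantities the documents do not give. That stands. A reader might infer that omitting baseline biases the result or invalidates the test, but the change-score comparison is unbiased under randomisation.

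Four other strong readings are tempting and not supported:

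- **A gain of about a fifth.** This needs equal SDs and r near 0.5. The entry criterion restricts the baseline, and on self-report the gain is then single-digit and can vanish.
- **That naming Week 8 adds precision.** It does not, because the 0/4/8 interaction already equals the Week 8 change difference. If the effect is complete by Week 4, a slope can even do slightly better: in simulation at r = 0.7 and N = 27 with equal SDs, signal-to-noise relative to 0/4/8 was 1.06 for baseline-adjusted Week 8 and 1.09 for the -4/4/8 slope.
- **That -4 weeks bounds the first SRS-2.** The design section speaks of "allowing up to four weeks from the date of consent to schedule and complete the initial screening process", but section 5 puts the SRS-2 before consent. The -4 coding is only an example.
- **That robust standard errors inflate type I error.** This follows only with a normal reference distribution, which section 9 does not state.

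It is also fair to say that the interaction is the obvious test. But section 9 does not say so, and nothing in it fixes the time value of the first SRS-2. If the observer form were primary, with two occasions only, coding would merely rescale the slope; the baseline point would remain.

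**Conclusion.** The concern holds as an efficiency and clarity point. The SRS-2 model in section 9 is valid but unadjusted for baseline. With the entry cut on self-report, adjustment would reduce variance by about 7% to 0% (N = 27) or 9% to 2% (N = 54). With no restriction and equal SDs it would be 22% to 6% or 24% to 8%. For a normal baseline the loss cannot exceed about 4% or 2%. These figures rest on assumed correlations of 0.5 to 0.8, an assumed cut at the median, and complete data.

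The undefined baseline record and visit coding are a separate matter of clarity. Under the illustrative -4/4/8 coding, 8 × slope recovers 57–71% of the Week 8 effect. The conflict between 27 and 54 randomised enters here only as two sample sizes and should be handled as its own finding.

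**What to change.** In section 9, for SRS-2:

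1. Constrain the baseline means to be equal between arms, or use baseline SRS-2 as a covariate with only post-baseline scores as responses. It should not be both covariate and response.
2. State that the screening/pre-screening SRS-2 is the baseline record, and reconcile the Screening Visit list, the Subject-Rated Measures list and Table II.
3. Name the Week 8 between-arm difference as the primary contrast. This is needed once baseline is a covariate, because the interaction would then compare the Week 4 and Week 8 effects. State how SRS-2 scores from early termination enter the model, for example at their actual assessment time or in the nearest scheduled visit.

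Optionally, state a t-based small-sample reference for the test.

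No new data are needed. The cost is SAP wording, including the early-termination rule, plus one degree of freedom and at most about 4% in variance.
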